## 8.6 ALLOSTATIC LOAD

Allostatic load will be determined based on laboratory results and clinical measures that will

Figure 3. TSST Procedures and Timeline		
TIME	EXPERIMENTAL PROCEDURE	STRESS ASSESSMENT
4:00-4:15pm	Acclimation period (15 minute duration)	Patient arrives and given relaxation tools (i.e. spa video, magazine, nature scenes)
4:16 Baseline (immediately following acclimation period)	Laboratory Stress measurements	Take cortisol, BP, HR, and assess SUD
4:28pm Immediately before TSST (12 minutes following baseline)	Laboratory Stress measurements	Take cortisol, BP, HR, assess SUD, and explain the task and give participant paper to write notes
4:33- 4:44pm (5 minutes following 2 nd lab measurements)	TSST	
5 minutes	Interview task	
5 minutes	Arithmetic task	
Post TSST stress assessments (12 minute increments)		
4:46pm Post TSST (2 minutes following TSST)	Post-TSST Assessment	Cortisol, BP, HR, SUD
4:58pm 12 mins post TSST	Post-TSST Assessment	Cortisol, BP, HR, SUD
5:10pm 24 mins post TSST	Final Post-TSST Assessment	Cortisol, BP, HR, SUD
Note: Patients more than 15 minutes late are unable to participate in the TSST and would need to be rescheduled.		

include the following; blood pressure, heart rate, total cholesterol, HDL cholesterol, body mass

index (BMI), C-reactive protein (CRP), DHEAS and interleukin-6 (IL-6). Cortisol will also be measured for those participating in the optional sub-study. We will use established methods to determine allostatic load. These methods use established clinical cutoffs to categorize biomarkers as being within normal ranges. For instance, a systolic blood pressure  $\geq 140$  mm/Hg and CRP  $\geq 3$  mg/L are values that are outside of normal ranges. The values for each biomarker will be coded into a dichotomous variable (1=above normal cutoff and 0=below normal cutoff). Scores for allostatic load will be calculated by summing dichotomous values for each biomarker.

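### Section 8.6 codes every allostatic load marker 1 when above its cutoff, which conflicts with its own normal-range wording and scores the wrong side of HDL and DHEAS, taking low values as adverse

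*Combined protocol and SAP*

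**What the plan says.** Section 8.6 names the components as "blood pressure, heart rate, total cholesterol, HDL cholesterol, body mass" index, then "C-reactive protein (CRP), DHEAS and interleukin-6 (IL-6"). Counting blood pressure once, that is eight markers. For sub-study participants, "Cortisol will also be measured for those participating in the optional sub-study", which may make nine.

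The scoring rule turns each marker, without exception, into a 0/1 code: "1=above normal cutoff and 0=below normal cutoff". The aggregation is an unweighted sum: "Scores for allostatic load will be calculated by summing dichotomous values for each biomarker".

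The purpose given for the cutoffs is different in kind: "These methods use established clinical cutoffs to categorize biomarkers as being within normal ranges". The two worked examples, a systolic pressure and a CRP threshold, "are values that are outside of normal ranges". In both, high is the abnormal side. No cutoff or direction is given for HDL or DHEAS, and no other section makes an exception for them.

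Section 2.6.2 describes allostatic load as an indicator of biological dysregulation. Sections 3.3 and 10.3 use it in sub-study Aims 2 and 3. In Aim 3 it is the outcome of the linear mixed model and of the comparisons of change between consecutive visits. Section 8.1.4 relates the TSC22D3/GILZ genotypes to it.

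**The concern.** A summed index of dysregulation works only if each 0/1 code points the same way. A rule of 1 for above the cutoff does that only for markers whose abnormal side is high. For a marker whose abnormal side is low, a healthy value earns a point and an abnormal value earns none. That marker then subtracts from the signal carried by the others.

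Section 10.3 expects only around 30-40 patients in the sub-study, so there is little room for avoidable measurement error in its main biological measure. The written rule also leaves the analyst in an awkward position: following it gives a score that contradicts its stated meaning, and silently correcting it departs from the plan.

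**Working it through.** The plan states no numerical property of the score, so there is no figure to reproduce. The check applies the written rule to the listed markers and compares the result with direction-aware coding.

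**Inputs from section 8.6.** Eight listed markers, or nine with cortisol; "1=above normal cutoff and 0=below normal cutoff" for each; unweighted sum.

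**Assumptions, not in the documents.** Low is adverse for HDL and DHEAS and high is adverse for the rest. Each marker is cut at its adverse threshold. Adverse prevalence is 20%, 35% or 50%, the same for every marker. The latent pairwise correlation is 0, 0.2 or 0.4.

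**Step 1: extremes.** Let A = 1 if a marker is adverse. Intended score S = sum of all A. Written score W = sum of A over the other markers + (1 - A) for HDL + (1 - A) for DHEAS.

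| Subject | Written, 8 | Intended, 8 | Written, 9 | Intended, 9 |
|---|---|---|---|---|
| Adverse on all | 6 + 0 = 6 | 8 | 7 + 0 = 7 | 9 |
| Adverse on none | 0 + 2 = 2 | 0 | 0 + 2 = 2 | 0 |

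Each reversed marker adds 1 - 2A to the error W - S. The error is therefore +2 if both are favourable, 0 if exactly one is adverse, and -2 if both are adverse.

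**Step 2: independent markers with equal variance v.** Eight markers: Cov(S, W) = 6v - 2v = 4v and Var(S) = Var(W) = 8v, so the correlation is 4/8 = 0.50. Nine markers: (7 - 2)/9 = 0.56. If only HDL is reversed among eight: (7 - 1)/8 = 0.75.

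**Step 3: correlated markers.** With common correlation r between the binary codes, for eight markers

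corr(S, W) = 4(1 + 7r) / sqrt[8(1 + 7r) x 8(1 + r)] = 0.5 x sqrt[(1 + 7r)/(1 + r)].

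At 50% prevalence, r = (2/pi) x arcsin(latent correlation). A latent correlation of 0.4 gives r = 0.262 and 0.5 x sqrt(2.834/1.262) = 0.75. A latent correlation of 0.2 gives r = 0.128 and 0.5 x sqrt(1.897/1.128) = 0.65.

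Simulation with 200,000 subjects per scenario and one shared latent factor agrees and covers the other prevalences:

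| Latent correlation | 8 markers | 9 markers |
|---|---|---|
| 0 | 0.50 | 0.56 |
| 0.2 | 0.63-0.65 | 0.69-0.71 |
| 0.4 | 0.73-0.75 | 0.79-0.81 |

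At latent correlations of 0.2-0.4, the score's correlation with the shared underlying factor falls from 0.67-0.85 to 0.42-0.63 (eight markers), or from 0.69-0.86 to 0.48-0.69 (nine).

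**Step 4: comparison with omission.** Leaving both markers out of the eight would give sqrt(6/8) = 0.87 under independence and up to 0.96 across the same scenarios. Under these assumptions the written rule does worse than dropping HDL and DHEAS.

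**Step 5: visits affected.** Section 7.1 plans the lipid panel at baseline only, while section 10.3 summarises allostatic load at baseline, day 85, day 225 and day 730 or off study. HDL therefore has no planned follow-up value, and the two-of-eight calculation describes baseline. If total and HDL cholesterol were simply left out later, DHEAS would be the one reversed marker among six, and the independent-case correlation would be (5 - 1)/6 = 0.67. The plan does not say how this gap is handled.

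**The case against.** The best defence is that the parenthetical is loose shorthand. The paragraph appeals to established methods, speaks of normal ranges, and illustrates the rule with two markers where high is abnormal. Section 2.6.2 supplies the intended meaning. On that reading the authors meant 1 for an abnormal value, and an experienced analyst would code HDL and DHEAS accordingly. This is probably what was intended, and it stands as an account of intent. It does not rescue the text. The section cites no source and gives no marker-by-marker rule, so the parenthetical is the only operational instruction, and it contradicts the sentences around it.

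Other limits also stand:

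- The adverse direction of HDL and DHEAS comes from clinical knowledge, not from the documents.
- The 0.50 end of the range needs independent markers, which sits poorly with an index of one underlying burden.
- If cortisol enters the sum, the reversed share is two of nine rather than two of eight.
- If DHEAS were cut at an upper reference limit, most men would score 0. The marker would then lose information and miss low values rather than fully reverse.
- The laboratory values can be recoded at analysis, so no data are lost.

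A reader might go further and infer that a racial difference could change sign, or that associations with relapse are distorted. The documents support neither. They give no HDL or DHEAS distribution by race, and no sign change has been shown. Section 10.3 plans no test of allostatic load against relapse: it compares RFS between racial groups. Section 8.1.4 relates genotypes to allostatic load and to relapse risk as separate questions. Only the general data-integration text in section 11.8 links allostatic load to outcomes.

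**Conclusion.** The stated coding rule is wrong as written. It conflicts with the paragraph's own purpose for the cutoffs and with the meaning given to the score in section 2.6.2. Taking low HDL and low DHEAS as adverse, the attainable extremes for all-adverse and all-healthy men shrink from 8 and 0 to 6 and 2. The written score tracks the intended one at about 0.50-0.75 (eight markers) or 0.56-0.81 (nine), over assumed prevalences of 20-50% and latent correlations of 0-0.4. None of those prevalences or correlations comes from the documents.

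The consequence is weaker exploratory analyses in sub-study Aims 2 and 3 and in the TSC22D3/GILZ work, with HDL affected mainly at baseline. It would be too strong to infer that the index is certain to be derived backwards: direction-aware coding was probably intended, and six of the eight markers are unaffected. The primary endpoint, its decision rules, safety monitoring and eligibility do not depend on the score. The text should be corrected before the score is derived.

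**What to change.** Replace the coding sentence in section 8.6 with: *1 = value on the adverse side of the marker's clinical cutoff, 0 = otherwise; HDL cholesterol and DHEAS are coded 1 when below the cutoff.*

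Add a short table giving, for each marker, the cutoff the team will use, its source and the adverse direction. State whether blood pressure counts once, and whether cortisol enters the sum for sub-study participants and, if so, in which direction. While editing, state how the score is formed at visits without a lipid panel.

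The cost is one sentence, one small table and a line or two of derivation code. No new data are needed, and there is no effect on patients or on the primary analysis.

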## **9 ADVERSE EVENT REPORTING**

For the purposes of this trial, “study vaccine” is defined as PROSTVAC-V/F.

### **9.1 INVESTIGATOR RESPONSIBILITIES**

Investigators are responsible for monitoring the safety of subjects who have entered this study and for assuring appropriate medical care is provided. Investigators are responsible for providing subjects who experience adverse events, especially SAEs that cause subjects to discontinue participation in the study, with appropriate medical care. Frequency of follow-up of any particular adverse event is left to the discretion of the investigator. Duration of follow-up and requirement for immediate SAE reporting (within 24 hours of becoming aware of the event) are described below.

### **9.2 DEFINITION OF ADVERSE EVENTS (AE)**

An AE is any untoward (unfavorable, harmful, or pathologic) medical occurrence in a subject administered an investigational product even if the event does not necessarily have a causal relationship with this treatment. An AE can therefore be any unfavorable and unintended sign (including an abnormal laboratory finding), symptom, or disease temporally associated with the use of a medicinal (investigational) product whether or not related to the investigational product (ICH E2A II/A/1, 21 CFR 312.32).

For the purpose of this clinical study, AEs include only treatment-emergent events which are either new or represent detectable exacerbations of pre-existing conditions. AEs may include, but are not limited to:

- Subjective or objective symptoms spontaneously offered by the subject and/or observed by the Investigator or study staff including laboratory abnormalities of clinical significance.
- AEs not previously observed in the subject that emerge during the protocol-specific AE reporting period, including signs or symptoms associated with prostate cancer that were not present before the AE reporting period
- Complications that occur as a result of protocol-mandated procedures and interventions.

For the purposes of this study, the following exceptions to the definitions above will **NOT** be considered an AE:

- **Pre-existing condition:** A pre-existing condition (documented on the medical history CRF) is not considered an AE unless the severity, frequency, or character of the event worsens during the study period.

- **Preplanned hospitalization:** A planned hospitalization is not considered an SAE, but rather a therapeutic intervention. However, if during the pre-planned hospitalization an event occurs, which prolongs the hospitalization or meets any other SAE criteria, the event will be considered an SAE. Surgeries or interventions that were under consideration, but not performed before enrollment in the study will not be considered serious if they are performed after enrollment in the study for a condition that has not changed from its baseline level. Hospitalizations for social reasons or due to long travel distances are also not SAEs.
- **Diagnostic testing and procedures:** Testing and procedures should not be reported as AEs or SAEs, but rather the cause for the test or procedure should be reported.

### 9.3 COLLECTING AND RECORDING ADVERSE EVENTS

The Investigator will monitor the occurrence of AE for each subject during the course of the study. All AEs (as defined above) reported by the subject, observed by the Investigator, or documented in medical records will be listed on the AE CRF, whether believed by the Investigator to be related or unrelated to the study vaccine.

All AEs must be reviewed, graded and causality determined by an Investigator listed on the form FDA 1572 at the research center reporting the event(s). Collection of AEs begins at the time the subject starts study treatment and continues for 28 days following administration of the last dose of study medication. If an SAE is present at the end of the reporting period, the SAE (and associated AEs and concomitant medications) should be followed to resolution or until the Investigator assesses the subject as stable, or the subject is lost to follow-up or withdraws consent. Resolution/stable means the subject has returned to baseline state of health or the Investigator does not expect any further improvement or worsening of the event.

Adverse event terms should be recorded concisely, using CTCAE v. 4 terms. When possible, a diagnosis (*i.e.*, disease or syndrome) rather than the component signs and symptoms should be recorded on the CRF (*e.g.*, congestive heart failure rather than dyspnea, rales, and cyanosis). However, signs and symptoms considered unrelated to syndromes or diseases are to be recorded as individual adverse events on the CRF (*e.g.*, if congestive heart failure and severe headache are observed at the same time, each event is to be recorded as an individual adverse event). The adverse event should not be recorded as a procedure or clinical measurement (*i.e.*, a laboratory or vital sign). The underlying reason for the procedure or the abnormal clinical measurements, and, whenever possible, a diagnosis, should be recorded.

Death is considered to be an outcome of an adverse event. The cause of death should be recorded on the AE CRF (*e.g.*, congestive heart failure with an outcome of death rather than the term “death”).

### 9.4 ASSESSMENT OF ADVERSE EVENTS

Investigators will assess the occurrence of AEs and SAEs at all subject evaluation time points during the study. All AEs and SAEs whether volunteered by the subject, discovered by study

personnel during questioning, or detected through physical examination, clinically significant laboratory test, or other means will be recorded in the subject's medical record and on the AE CRF and, when applicable, on the SAE report form.

Each recorded AE or SAE will be described by its duration (i.e., start and end dates), severity, suspected relationship to the investigational product, and any actions taken. Any SAE that occurs after the subject signs informed consent, irrespective of the treatment received by the subject, must be reported to the SIS Unit within 24 hours of the investigator learning of the event.

## 9.5 DEFINITION OF EXPECTED AND UNEXPECTED EVENTS

### 9.5.1 Expected Events

Expected events are those that have been previously identified as resulting from administration of the investigational product. For the purpose of this study, an AE is considered expected when it appears in the current adverse event list, the IB, the package insert or is included in the ICF as a potential risk. Injection site reactions such as pain, redness, swelling, induration, and pruritus, or systemic injection reactions such as fever  $\geq 104^{\circ}\text{F}$ ; myalgia, headache, nausea, fatigue lasting less than 72 hours are expected events for PROSTVAC-V/F.

If, however, the investigator considers an expected event to be unexpectedly severe or more frequent than usual for a patient with prostate cancer following prostatectomy the event will be captured on the AE CRF. Similarly, if the event is associated with PROSTVAC-V/F, and is unexpectedly severe, it will also be recorded on the AE CRF.

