## 2.5 POTENTIAL BENEFITS AND RISKS TO HUMAN SUBJECTS

The intent of vaccination with PROSTVAC-V/F is to induce an immune response to PSA, and other prostate- and tumor-specific antigens. In the randomized, placebo controlled Phase 2 trial, an over-all survival benefit among patients who received PROSTVAC-V/F was observed. It is unknown whether PROSTVAC-V/F will provide this benefit to subjects participating in this trial, as this product is still currently in development. Benefits of this trial also include the potential boosting (or acquisition) of protective immunity against smallpox.

Based on clinical experience with PROSTVAC-V/F in Phase 2, adverse reactions are expected to be minimal. A local injection site reaction is typical, and comparable to those seen with other modern vaccines. Potential adverse reactions attributable to the administration of PROSTVAC-V/F at  $\geq 50\%$  frequency include injection site reactions (pain, swelling, induration, and redness), and at  $\geq 10\%$  frequency include headache, fatigue, myalgia, and nausea; the majority of events of Grade 1 and 2 in severity.

The priming vaccination with PROSTVAC-V is with a vaccinia-based replicating virus. Special wound pre-cautions are required. The vaccinia virus has been used in millions of people to eliminate smallpox. In this trial it is given subcutaneously, not by dermal scarification, and local injection site reactions are much less severe, and viral shedding is minimal. However, there are still risks of inadvertent infection of other body sites (through scratching), or transfer of infection to others. Special bandage precautions are required, and subjects need to avoid contact with small children  $<3$  years of age, individuals who are immunocompromised or are receiving

immunosuppressive therapies, and pregnant or lactating women (for 3 weeks). With smallpox vaccine programs in vaccinia-naïve subjects immunized by dermal scarification, inadvertent inoculation occurred approximately 1/6,000 vaccinations. Subjects in this trial will be given detailed instructions on proper care of the injection site and rules of hygiene to prevent inadvertent inoculations and transmission of vaccinia virus.

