## 9.10 EXPEDITED REPORTING REQUIREMENTS FOR SERIOUS ADVERSE EVENTS AND EVENTS OF SPECIAL INTEREST

All events described in section 9.8 and 9.9 must be submitted to the SIS Unit within 24 hours of the investigator learning of the event following the SOPs outlined in the CTO 102377 Operations Manual.

The SIS Unit will be responsible for processing these events for reporting to the applicable regulatory and oversight authorities including the IRB, DSMC and FDA.

All SAEs and events of special interest must be reported to Bavarian Nordic, Inc. within 24 hours by fax or email to:

Bavarian Nordic, Inc.  
Attn: Drug Safety and Pharmacovigilance Designee  
[contact]

Email: [[contact]](mailto:[contact])

Any suspected, unexpected SAE, skin lesion positive for vaccinia, pregnancy of a female partner, or accidental transmission of vaccinia virus must be reported to the FDA as soon as possible and no later than 7 days (for a death or life-threatening event) or 15 days (for all other SAEs) after the investigator's or institution's initial receipt of the information.

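### Section 9.5.1 conflicts with 9.3 and 9.4 on whether ordinary expected vaccine reactions go on the AE CRF, and its fever limit does not fit 2.4.4.1 and 2.5

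*Combined protocol and SAP*

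**What the plan says.** Three sections of the combined protocol and SAP govern what is recorded.

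- Section 9.3: all AEs, however they come to notice, "will be listed on the AE CRF, whether believed by the Investigator to be related or unrelated to the study vaccine". Expected events are not exempted.
- Section 9.4: AEs and SAEs that are volunteered, found on questioning, examination or laboratory testing, "or other means will be recorded in the subject's medical record and on the AE CRF".
- Section 9.5.1: after listing the expected reactions, it says an event will be captured on the AE CRF if the investigator "considers an expected event to be unexpectedly severe or more frequent than usual for a patient with prostate cancer following prostatectomy". It adds that "if the event is associated with PROSTVAC-V/F, and is unexpectedly severe, it will also be recorded on the AE CRF".

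The expected list in 9.5.1 covers injection-site pain, redness, swelling, induration and pruritus, "or systemic injection reactions such as fever" of 104°F or above, and myalgia, headache, nausea and fatigue, with a 72-hour limit on duration.

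Section 2.5 describes the same reactions as the vaccine's most common effects. At 50% or higher, "frequency include injection site reactions (pain, swelling, induration, and redness"; at 10% or higher, headache, fatigue, myalgia and nausea. It expects reactions to be minimal and mostly Grade 1 or 2.

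Toxicity is a secondary objective (3.2), analysed by tabulation of CTCAE grade and type (10.2.2).

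**The concern.** Expectedness normally decides how quickly an event is reported, not whether it is recorded. The two sentences in 9.5.1 attach it to recording. They open with a contrasting conditional, and they add nothing to 9.3 and 9.4 unless ordinary expected events are being left off the form. As the more specific rule, they are what a coordinator faced with a red injection site might reasonably follow.

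The frequency criterion is also hard to apply. It compares the event with what is usual in men after prostatectomy, which gives no benchmark for a vaccine injection-site reaction. For those reactions, capture would rest on each investigator's opinion of what is unexpectedly severe.

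At stake is the completeness of the toxicity table, and its comparability between sites and investigators, for the mild and moderate events that 2.5 says make up most of the vaccine's effects. The fever limit raises a separate question: which fevers count as expected when a serious one has to be classified under 9.10.

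**Working it through.** The plan gives no figure to reproduce on this point. The check compares the sections and then sizes the possible gap.

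**1. Recording rules side by side**

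| Section | Ordinary expected reaction on the AE CRF? |
|---|---|
| 9.2 (exceptions to the AE definition) | Exempts pre-existing conditions, preplanned hospitalizations, and tests and procedures. Expected vaccine reactions are not exempted. |
| 9.3 | Yes |
| 9.4 | Yes |
| 9.5.1 | By implication no: capture is stated for unusual severity or frequency |

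Section 9.5.1 neither withdraws nor refers to 9.3 or 9.4, so both instructions are in force.

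**2. Which events are affected**

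Section 2.5 names eight reactions: injection-site pain, swelling, induration and redness, and headache, fatigue, myalgia and nausea. All eight are on the 9.5.1 expected list. The events whose recording is in doubt are therefore the most frequent ones.

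**3. Size of the possible gap**

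Inputs: 33 men planned (10.1); frequency of at least 50% for injection-site reactions and at least 10% for each of the four systemic reactions (2.5).

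- Injection-site reactions: 0.50 × 33 = 16.5, so about 16 men or more.
- Each of headache, fatigue, myalgia and nausea: 0.10 × 33 = 3.3, so about 3 men or more.

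If 9.3 and 9.4 are followed, the number unrecorded is 0. If every site follows 9.5.1 and no such reaction is judged unusual, it is the counts above. The gap is therefore 0 to about 16 or more for injection-site reactions, and 0 to about 3 or more for each systemic reaction.

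**4. The fever limit**

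- 104°F is (104 − 32) × 5/9 = 40.0°C.
- Section 9.5.1: fever at or above this limit is expected, with no upper bound. Lower fever is not named.
- Section 2.4.4.1: fever after vaccinia is among the normal events, with no temperature given.
- Section 2.5: reactions are expected to be minimal and mostly Grade 1 or 2. Fever is in neither frequency list.
- Section 9.5.2: an event is unexpected if it departs in nature, intensity or frequency from the reference documents.

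Read literally, the 9.5.1 list contains the highest fevers and leaves out milder ones, and 9.5.1 and 9.5.2 could classify the same fever differently.

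**5. Where the label has an effect**

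Section 9.10 requires FDA reporting, within 7 or 15 days, of "Any suspected, unexpected SAE, skin lesion positive for vaccinia, pregnancy of a female partner" and accidental transmission. Here expectedness decides whether an SAE enters the expedited FDA route.

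**The case against.** The strongest reply is that 9.3 and 9.4 are unconditional, 9.2 lists its exceptions and expected reactions are not among them, and 9.5.1 contains no word that restricts capture to unusual events. A reader might infer that 9.5.1 exempts ordinary reactions and that the toxicity record will omit the vaccine's main effects. The documents do not support that: two sections require the recording, and one implies otherwise. Omission is a risk, not an established result. What remains is that sites can follow either instruction.

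A reader might also infer that a high fever could escape the safety stopping count. The 10.1 rule counts possibly related toxicity of Grade 3 or above whatever its expectedness, and even 9.5.1 captures an unexpectedly severe event. The documents do not give the CTCAE grade of a 104°F fever. That inference is not made here.

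On expedited reporting, 9.10 sends all SAEs to the SIS Unit and to the manufacturer within 24 hours, expected or not, and 9.5.2 allows reclassification on intensity. This confines the effect of the fever label to the FDA clause.

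On the limit itself, the 9.5.1 list gives examples and is not exhaustive, and expectedness also depends on the adverse event list, the Investigator's Brochure, the package insert and the consent form. Lower fever is therefore not shown to be unexpected. A majority of Grade 1 or 2 events does not rule out a severe expected one. A reversed inequality is plausible but unproven. The mismatch with 2.4.4.1 and 2.5 still needs an explanation.

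**Conclusion.** The point holds as an internal contradiction. Sections 9.3 and 9.4 require every AE on the CRF, while 9.5.1 implies that expected reactions are captured when unusually severe or frequent. Depending on which rule sites follow, the toxicity table could lack injection-site reactions in anywhere from 0 to about 16 or more of 33 men, and each of four systemic reactions in 0 to about 3 or more.

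The upper figures assume that all 33 men are dosed, that the section 2.5 frequencies are per man and carry over to this population, that 9.5.1 is followed at every site, and that no reaction is judged unusual. They are not a forecast.

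The fever limit is a second, smaller inconsistency. Its identifiable consequence is the possible classification of a serious high fever under the 7/15-day FDA clause.

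Neither matter touches the primary endpoint, the sample size, the efficacy decision rule or the stopping criteria. Both are worth correcting because the correction is cheap and mild reactions not entered at the time may be hard to recover.

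**What to change.** In 9.5.1, replace the two conditional-capture sentences with a statement that every AE, expected or not, is graded and recorded under 9.3 and 9.4, and that expectedness is used only for expedited reporting under 9.10.

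Check the fever limit against the Investigator's Brochure and reconcile it with 2.4.4.1, 2.5 and 9.5.2, so that all four sections classify a given fever in the same way.

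The cost is a few sentences in an amendment and a memo to sites. The downside is a few more AE lines per man, for events that investigators already assess at study visits under 9.4.
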